4.3. Secondary analyses

The above modelling strategy will be repeated to compare the rate of improvement (RCSI) in GAD-7 anxiety symptoms, and RCSI in depression symptoms only in the cases who attended at least one treatment session. We will also compare outcome expectancy, dropout rates and adverse effects between groups, and compare characteristics between those who attended at least one treatment session versus those who dropped out following assessment. For both TherapyMatch-D and control groups, we will estimate the proportions of participants who had RCSI post-treatment, and who completed/dropped out of treatment. We will also calculate and report effect sizes for each of the symptom measures (PHQ-9, GAD-7, WSAS) using Cohen's *d* metric (Cohen, 1988), based on mean differences between groups. Treatment attendance, completion, and dropout rates will be presented diagrammatically and based on CONSORT guidelines. To quantify any potential adverse effects related to the trial, we will also calculate a rate of reliable deterioration in patients across both arms of the trial. Further, we will use the data collected to identify complex cases (see StratCare Trial from Delgadillo et al., 2021) and control for variability in complex cases across Talking Therapies sites.

We will examine adherence to the TherapyMatch-D model using the full study sample of participants with a differential treatment response across both arms. Each therapist's Treatment-Matching Precision Score (TMaP) will be calculated, which is a statistical measure of agreement between their observed treatment selection and the recommendations made using the prognostic algorithm. In the experimental group, this would represent the agreement of patients accepting the recommended treatment. In the control group, this is the post-hoc analysis of the agreement the optimal treatment that the prescriptive algorithm would recommend (which patients did not receive, since they were in the control group) and the actual treatment selected via shared decision making. A comparison of mean TMaP scores between groups will be done using parametric or non-parametric tests, depending on the distribution of TMaP scores.

The wider cohort dataset (i.e., non-differential responders who consented to take part in this trial) will be used to examine changes in treatment recommendation patterns over time and treatment outcomes, modelling longitudinal changes in the prevalence of treatment recommendation. These additional analyses with non-differential responders will serve only to maximize the use of available data to inform a future trial, but the results will not be included in the main analyses.

Basic demographic data collected from therapists providing the two psychological treatments to describe the overall workforce (e.g., age, gender, caseload, and qualifications) will be reported in the study, to identify any potential differences in staff providing the intervention. No further analysis of this data is planned a priori. If large differences were found between therapists providing interventions, post-hoc exploratory analysis may be conducted as part of a feasibility trial that may inform future research.

6. Ethical considerations

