4.6 Eligibility criteria

Talking Therapies Sites

Inclusion criteria

- Talking Therapies site routinely providing CBT and PCE-CfD at step 3.
- Service manager provides informed written consent to enlist the Talking Therapies site and names a lead Local Principal Investigator.

Exclusion criteria

• Lack of any therapists or patients providing informed consent, or lack of consent by service manager.

Therapists/Counsellors

Inclusion criteria

- Be employed by a participating Talking Therapies service on a permanent contract, or be employed
 as temporary staff with a contract that is at least as long as the expected timescale for the project (1 year)
- Hold a UK recognized qualification and be approved by Talking Therapies to carry out routine assessments in an Talking Therapies service
- Attended a group/individual training on how to utilize the computer programme TherapyMatch-D computer programme.

Exclusion criteria

- Employment contract is shorter than the minimum expected timescale for the study (1 year).
- Currently in training (since they are not yet fully qualified to carry out routine assessments)

Patients

Inclusion criteria

Adults (18 years of age or older).

- With depression (defined as scoring at least 10 on the PHQ-9), including those with co-morbid anxiety and those taking antidepressant medication (we will monitor and examine potential confounding effects of comorbidity and medication).
- Seeking mental health care in Talking Therapies services at Step 3 (normally via self-referral, GP referral or stepped up from Step 2 low intensity Talking Therapies treatment).
- Deemed eligible for high intensity treatment in Talking Therapies by assessing therapists (patients who do not improve at the earlier steps of care), regardless of any prior mental health treatment from Talking Therapies or elsewhere (we will monitor and examine potential confounding effects of prior treatment and baseline severity).
- Able to take part in the initial assessment in English without the need of interpreters or substantial communication adaptations.

Exclusion criteria

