4.7 Primary and Secondary Outcomes and Measures

Primary outcome and measure

This study aims to pilot effectiveness of using a targeted prescription to guide treatment selection to improve clinical outcomes in depression relative to AAU, for which the main outcome variable is RCSI in depression. Effectiveness will be measured by the Patient Health Questionnaire-9 (PHQ-9) at the end of the treatment period (last session of CBT or PCE-CfD), with adjustment for baseline depression.

The PHQ-9 (Kroenke et al., 2001) is a brief measure commonly used to monitor the severity of depression and response to treatment. Each of the nine items is scored on a 0-3 scale. Item scores are summed to give an overall severity rating (range 0-27). The PHQ-9 has been validated for use in primary care (Kroenke et al.,2010), with adequate sensitivity (88%) and specificity (88%) estimates for the detection of major depressive disorder using a cut-off score ≥ 10 . RCSI was determined based on the method described by Jacobson and Truax (1991), by combining reliable change index (PHQ ≥ 6) and diagnostic cut-offs (PHQ-9 < 10).

Secondary outcomes and measures

The secondary outcome measures aimed to measure feasibility (adherence to the recommendation provided by the targeted prescription algorithm and outcome expectancy) and effects (anxiety, functional impairment, drop-out rates and adverse events). The specific variables were chosen as additional ways to measure improvement in clinical outcomes, to control for complexity and those variables that were identified to predict a differential response to treatment in the development of the targeted prescription

algorithm, and therefore needed to provide a targeted prescription recommendation of treatment (Delgadillo & Gonzalez Salas Duhne, 2020).

The specific measures for the secondary outcomes are:

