- Adherence to treatment selection recommendation. In cases with differential response in the experimental arm (TherapyMatch-D), we will monitor and quantify adherence between the treatment selection recommendation and the actual therapy selected by the patient and therapist. This will be measured by a question embedded in the TherapyMatch-D computer programme. After clinicians input clinical and demographic data into the computer programme (at assessment), the computer programme will immediately provide a personalized treatment recommendation where appropriate (if they are part of the TherapyMatch-D intervention group and they are deemed to have a differential response according to past research, which will be determined using the TherapyMatch-D computer programme). Following this recommendation, clinicians will be asked to input on the same computer programme at the end of the session if a treatment has been selected by the patient and therapist, and the specific selected treatment. Clinicians will be asked to write the reasons why they selected a particular treatment, only where the recommended treatment from the computer programme and the selected treatment through shared decision making do not match.
- Outcome expectancy (OE). Patients' expectation of therapeutic outcome will be measured by asking "At this point in time, how confident are you that this kind of treatment will work for you on a scale of 0 (not at all) to 10 (definitely)?" There is a reliable relationship between positive expectancy for therapy and better treatment outcomes (Constantino et al., 2018). Scores of 5 or below on this scale are indicative of low expectancy and therefore higher risk of poorer treatment outcomes (Delgadillo et al., 2016).
- Anxiety. The Generalized Anxiety Disorder (GAD-7; Spitzer et al., 2006) is a seven-item measure of common anxiety symptoms. Each item is scored on a 0-3 scale and these are summed to give an overall severity rating (range 0-21). The GAD-7 has been found to be a reliable screening tool for anxiety disorders such as generalized anxiety, social phobia, post-traumatic stress and panic disorder (Kroenke et al., 2007). A cut-off score ≥ 8 in this measure has been shown to detect an anxiety disorder with adequate sensitivity (77%) and specificity (82%).

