5.2. Primary analysis

Patient-level clinical outcome data will be analysed using logistic multilevel modelling conducted according to the intention-to-treat principle according to CONSORT guidelines for Cluster RCTs. Researchers will be blinded to the group allocation while analysing the trial data.

The primary outcome will be defined as reliable and clinically significant improvement (RCSI) in depression symptoms (PHQ-9) after treatment, based on the method described by Jacobson and Truax (1991). A 3-level model will be applied, with patients nested within therapists, nested within Talking Therapies sites, and post-treatment RCSI in depression (PHQ-9) symptoms as the dependent variable. Group (TherapyMatch-D vs. usual care) will be entered as a level-2 predictor, along with baseline PHQ-9 as a level-one covariate. This method will enable us to determine whether TherapyMatch-D is associated with a greater treatment effect (depression symptom reduction) by comparison to usual care and will be specifically run in the target sample of patients identified as having a differential response to treatment. The three-level model will account for the nested structure of the data, as appropriate within a cluster trial design. Given the small sample sizes of this pilot trial, it is unlikely the estimates of random effects for site and therapist will be reliable, but this data may be used to guide subsequent research. If the site and therapist random intercepts are not statistically significant, a one-level parsimonious multivariate regression model will be estimated as a sensitivity analysis. Adjusted odds ratios and confidence intervals will be reported as a primary effect sizes. In addition, we will also report the results in the best fitting model following analyses of goodness of fit to find the most parsimonious model.

We acknowledge that some patients might decide to switch from one therapy to another following allocation in either arm of the trial (i.e., patient allocated to CBT after consenting to treatment asks to switch to PCE-CfD), as occurs in routine practice occasionally. In this pilot trial, we will report the frequency of this occurrence and circumstances. Cases will be included in the primary analysis (as part of the

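### Cohen's d for PHQ-9, GAD-7 and WSAS has no stated baseline or site adjustment, and the repeated GAD-7 RCSI model names only baseline PHQ-9 as covariate

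*Protocol*

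**What the plan says.** The Secondary analyses section (numbered 4.3, but placed under section 5) commits to two things relevant here.

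- **Effect sizes.** The team will "calculate and report effect sizes for each of the symptom measures (PHQ-9, GAD-7, WSAS"), as Cohen's d "based on mean differences between groups". The text does not say whether the means are last-session scores, change scores or adjusted means, and it mentions no site term. Functional impairment is a secondary objective in section 3.2, and the synopsis lists a between-group comparison of it without a method. This d is therefore the only method described for WSAS.
- **GAD-7.** "The above modelling strategy will be repeated to compare the rate of improvement (RCSI) in GAD-7 anxiety symptoms". The strategy referred to is the three-level logistic model of section 5.2, with arm entered "along with baseline PHQ-9 as a level-one covariate". No other baseline covariate is named.

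The primary outcome is treated differently: section 4.7 has it measured "with adjustment for baseline depression", and section 5.2 reports adjusted odds ratios from a model that allows for nesting.

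On entry, section 4.6 takes patients "With depression (defined as scoring at least 10 on the PHQ-9), including those with co-morbid anxiety". Anxiety is allowed but not required, and there is no GAD-7 minimum. For GAD-7, section 4.7 says: "A cut-off score ≥ 8 in this measure has been shown to detect an anxiety disorder". RCSI is defined only for PHQ-9, by "combining reliable change index (PHQ ≥ 6) and diagnostic cut-offs (PHQ-9 < 10"). No reliable change value is given for GAD-7. Section 4.8 has PHQ-9, GAD-7 and WSAS all completed at assessment.

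**The concern.** With 3-5 sites per arm, the arms can easily differ at baseline by chance. A d computed from unadjusted group means carries part of that difference into the reported effect, although the scores needed to remove it are already in the dataset. In the GAD-7 model, baseline PHQ-9 is only a proxy for where a patient starts on GAD-7.

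The transfer of RCSI to GAD-7 also loses a property of the primary outcome. The PHQ-9 entry threshold equals the PHQ-9 recovery cut-off, so every entrant can achieve the primary outcome. GAD-7 has no matching entry threshold.

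No hypothesis is tested (section 3.3), so the estimates themselves are what the pilot delivers. Section 5.1 says the clusters are recruited so that a definitive trial can be sized. Avoidable noise in those estimates is what is at stake.

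**Working it through.** **1. The plan's own figure.** Section 5.1: 216 × 0.30 = 64.8, stated as 64 per arm; 432 × 0.30 = 129.6, stated in the synopsis as 128 in total. These agree apart from rounding. I use n = 64 per arm and k = 3 to 5 sites per arm.

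**2. Assumed inputs, not in the protocol.** ICC of the baseline score 0.02-0.05; correlation r between assessment and last-session score 0.5, with range 0.3-0.7.

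**3. SD of the chance baseline difference between arms, in score SDs:** sqrt(2 × (ICC/k + (1 − ICC)/64)).
- ICC 0.02, k = 5: sqrt(2 × (0.0040 + 0.0153)) = 0.197
- ICC 0.05, k = 3: sqrt(2 × (0.0167 + 0.0148)) = 0.251

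**4. Share entering an unadjusted d of last-session scores:** r × imbalance.

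| r | low (0.197) | high (0.251) |
|---|---|---|
| 0.3 | 0.059 | 0.075 |
| 0.5 | 0.098 | 0.126 |
| 0.7 | 0.138 | 0.176 |

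**5. If change scores were meant.** With equal SDs at both times, the imbalance enters as (r − 1) × imbalance. At r = 0.5 that is −0.098 to −0.126, the same size with the sign reversed. Across r = 0.3 to 0.7 the absolute range is again 0.06-0.18. Change scores do not remove the problem.

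**6. Gain from adjustment.** Adjusting for the scale's own baseline multiplies the patient-level standard error by sqrt(1 − r²).
- r = 0.5: sqrt(0.75) = 0.866, a cut of about 13%
- r = 0.3: sqrt(0.91) = 0.954, about 5%
- r = 0.7: sqrt(0.51) = 0.714, about 29%

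**7. Who can meet RCSI.**
- PHQ-9: the lowest entry score is 10, and 10 − 6 = 4, which is below 10. Every entrant can qualify.
- GAD-7, if RCSI requires crossing from 8 or above to below 8: nobody starting at 0-7 can qualify.
- GAD-7, if the PHQ-9 form is copied (reliable fall and final score below 8): the starting score must be at least the reliable change value, which the protocol does not give.

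| Assumed reliable change | Starts below 8 that can qualify | Starts that cannot |
|---|---|---|
| 4 | 4-7 | 0-3 |
| 5 | 5-7 | 0-4 |
| 6 | 6-7 | 0-5 |

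**The case against.** The strongest reply is that the text is brief rather than wrong. It does not call the means raw, and repeating a modelling strategy can naturally mean swapping in the outcome's own baseline. An SAP, not shown here, could settle both. The protocol also promises to examine confounding by comorbidity and baseline severity (section 4.6), to stratify sites (section 4.4) and to control for complex cases (Secondary analyses). What stands is that unadjusted means are an inference. But taken as written, the plan gives d no baseline or site term and the GAD-7 model the wrong scale's baseline. None of the other commitments names baseline GAD-7 or WSAS as a covariate.

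Several stronger readings are tempting, and the document does not support them.

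- **That all secondary symptom outcomes lack their own baseline.** PHQ-9 has its own in the primary model and in the repeat among attenders. GAD-7 RCSI uses the patient's own start through the reliable change element.
- **That the estimates are biased.** The imbalance has mean zero over randomisations, so it costs precision.
- **That the shift is more than half of a plausible effect.** The OR of 1.40 in section 2 (d = ln 1.40 × √3/π = 0.19) comes from stratified versus stepped care, a different intervention. The OR of 2.33 (d = 0.47) compares optimal with suboptimal treatment. Neither is this trial's arm contrast.
- **That nobody starting below 8 can improve, or that the GAD-7 effect shrinks by a known amount.** The first needs a crossing rule the protocol does not write; the second needs the share starting below 8, which it does not give.

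Keeping all patients in the GAD-7 denominator is also a legitimate intention-to-treat quantity.

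**Conclusion.** The point holds as a modest, cheaply corrected weakness. As written, d for the three scales has no stated baseline or site adjustment, and the GAD-7 RCSI model names only baseline PHQ-9. Under the assumed ICC and correlations, chance imbalance typically moves an unadjusted d by about 0.10-0.13 (0.06-0.18), and own-baseline adjustment would cut the patient-level standard error by about 13% (5-29%). The site-level gain is not quantified.

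Separately, the GAD-7 RCSI denominator includes patients who start below 8. All of them are unable to qualify under a crossing rule; under an end-state rule with an assumed reliable change of 4-6 points, those starting at 0-3 to 0-5 are unable. How many such patients there will be is unknown. The affected quantities are secondary estimates in a pilot that tests no hypothesis, and the primary odds ratio is untouched.

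**What to change.** - **Each of PHQ-9, GAD-7 and WSAS:** model the last-session score on arm and the same scale's assessment score, with a random site effect, or use a cluster-level analysis. Site should not be a fixed effect, because arm is nested in site and its effect could then not be estimated. Report the adjusted difference divided by the pooled baseline SD as d, with a confidence interval that reflects the number of sites (for example on sites minus 2 degrees of freedom: 6 − 2 = 4 to 10 − 2 = 8).
- **GAD-7 RCSI model:** name baseline GAD-7 as covariate, and write out the GAD-7 RCSI rule, including its reliable change value.
- **GAD-7 RCSI denominator:** report the result among patients scoring at least 8 at assessment alongside the all-patient result. The restriction answers a different question, so it should not replace the all-patient figure.

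The cost is analysis wording only, since every baseline score is already collected. The downside is a smaller denominator in the restricted GAD-7 result.

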3.3. Hypotheses

As a pilot study, no hypothesis testing is undertaken.

4. Methods

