4.4 Randomisation

Randomisation will take place on a site level (cluster). Each participating Talking Therapies site will be stratified and clustered according to demographics and then randomised using electronic randomisation software to either TherapyMatch-D (experimental) or AAU (control) condition. The aim of stratification is to control for sociodemographic characteristics as a potential confounding variable, and to identify a maximally diverse sample.

A site randomisation design has been adopted to minimise the chance of contamination which may occur if randomisation was applied at therapist or patient-level, since it is possible that a clinician who is familiar with the TherapyMatch-D model may apply this knowledge in AAU cases, or share this knowledge with other clinicians from the AAU group. This is particularly relevant in an Talking Therapies service because patients' clinical and demographic data are routinely available to all clinicians. Patients and clinicians will not be blinded to their allocation by virtue of the design.

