5.1. Sample size calculation

Pilot trials do not require a formal sample size calculation. However, a sample of at least 64 participants per arm is desirable (Teare et al., 2014) for a binary outcome in a pilot trial. We will aim to recruit 6-10 clusters (3-5 sites randomised in each arm) to allow subsequent sample size calculation for a definitive RCT. Within each Talking Therapies site, we will aim to recruit a minimum of 1 therapist that carry out routine assessment (maximum of 2 therapists per site). Each Talking Therapies site will aim to recruit 64 patients, For this, a total of 432 patients would be screened (216 patients per arm). As we expect approximately 30% of patients across sites to have a differential response, we estimate there would need to be 216 patients screened (64 patients per arm; 216*30% = 64). This calculation is based on the assumption of equal availability for treatment. As a pilot trial, any differences in treatment offer and waiting time for the different treatments will be reported and considered for potential subsequent research.

Overall, we will aim to recruit a minimum of 6-10 therapists that carry out routine assessments across the 6-10 Talking Therapies services (1 to 2 per Talking Therapies service). Between the 6 to 20 therapists, we expect that they will assess at least 432 during a 1-year study period, which would require each therapist to assess 1 to 2 cases per week on average.

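### The adherence comparison uses therapist-level TMaP scores although sites are randomised, so it overstates precision where a site contributes two therapists

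*Protocol*

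**What the plan says.** Protocol section 4.4 fixes the unit of allocation: "Randomisation will take place on a site level (cluster"). Section 5.1 gives the numbers: "We will aim to recruit 6-10 clusters (3-5 sites randomised in each arm"), and within each site "we will aim to recruit a minimum of 1 therapist that carry out routine assessment (maximum of 2 therapists per site"). That makes 6 to 20 therapists in all, or 3 to 10 per arm.

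The secondary analyses (headed 4.3, but placed after 5.2) set out a separate method for adherence among differential responders in both arms. "Each therapist's Treatment-Matching Precision Score (TMaP) will be calculated", as a measure of agreement between the therapy selected and the one the algorithm recommends. In the control arm the recommendation is worked out afterwards. Then: "A comparison of mean TMaP scores between groups will be done using parametric or non-parametric tests, depending on the distribution of TMaP scores".

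Section 5.2 uses a three-level model for the primary outcome and justifies it by the cluster design. The secondary analyses carry that model over by name to RCSI on the GAD-7 and to RCSI in depression among patients who attended at least one session. They do not carry it over to TMaP.

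Section 3.3 states: "As a pilot study, no hypothesis testing is undertaken".

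**The concern.** Two therapists at one site share the allocation and the local conditions that steer treatment choice. Section 4.8 says that selection in the control arm depends partly on which treatments are available and on supervisors' advice, and both are likely to be common to a site. If their scores are correlated, a two-group test on therapists uses too small a standard error and too many degrees of freedom. A confidence interval built on the same scores would be too narrow to the same extent.

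Adherence is the first feasibility item listed in section 3.2. The pilot is meant to inform a definitive trial, which needs an adherence difference with honest uncertainty. The choice between a parametric and a rank test would also rest on the shape of 3 to 10 scores per arm, which cannot be judged from so few values.

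**Working it through.** **The plan's own figure.** Section 5.1: 216 × 0.30 = 64.8 differential responders per arm, stated as 64. This reproduces. With two therapists per site, 64/6 ≈ 11 patients per therapist at 3 sites per arm and 64/10 ≈ 6 at 5 sites per arm. No alpha, power or intraclass correlation (ICC) is given for the TMaP comparison.

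**Form of the error.** With two therapists per site and correlation ICC between their scores, the variance of an arm mean is multiplied by 1 + (2 − 1) × ICC = 1 + ICC. The degrees of freedom are also overstated:
- 3 sites per arm: 12 − 2 = 10 on therapists, against 6 − 2 = 4 on sites.
- 5 sites per arm: 20 − 2 = 18 against 10 − 2 = 8.

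With one therapist per site, therapist and site coincide and neither problem arises.

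**Size, from simulated null trials.** Assumptions, none of them in the protocol: two-sided 0.05; score taken as the proportion matched; true match rate 50%; therapist SD 0.3 and site SD 0–1.2 on the logit scale; two therapists at every site. Percentage of null trials with p < 0.05 (40,000 per row):

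| Sites per arm | Site SD | Correlation of the two scores | t-test on therapists | t-test on site means |
|---|---|---|---|---|
| 3 | 0 | 0 | 5.2 | 4.7 |
| 3 | 0.2 | 0.08 | 5.9 | 4.9 |
| 3 | 0.4 | 0.25 | 8.6 | 5.0 |
| 3 | 1.2 | 0.72 | 16.8 | 5.8 |
| 5 | 0 | 0 | 5.2 | 5.3 |
| 5 | 0.2 | 0.05 | 5.8 | 5.1 |
| 5 | 0.4 | 0.17 | 7.2 | 5.2 |
| 5 | 1.2 | 0.60 | 13.6 | 5.3 |

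A rank test on therapists over site SD 0.4–1.2 gives about 6–13% at 3 sites per arm and 6–12% at 5.

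A site SD of 0.4 is a small patient-level correlation: 0.4² / (0.4² + 0.3² + π²/3) = 0.16/3.54 = 0.045. It becomes 0.17–0.25 between therapist scores because each score averages several patients.

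**Check with a different model.** With normally distributed therapist scores and two therapists per site, the t-test error at 3 and 5 sites per arm is:
- ICC 0.05: 5.6% and 5.4%
- ICC 0.1: 6.2% and 6.7%
- ICC 0.2: 7.8% and 7.8%
- ICC 0.3: 8.3% and 9.2%
- ICC 0.5: 12.5% and 11.6%

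If some sites have one therapist and some two, it is 5.1–5.7% at ICC 0.05 and 8.1–9.3% at 0.5. With one therapist per site it is 4.7% and 4.9%.

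**Rank-test floor.** The smallest exact two-sided p is 2/C(2n, n). For 3 v 3 it is 2/20 = 0.10, for 4 v 4 it is 2/70 = 0.029, and for 5 v 5 it is 2/252 = 0.008.

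**Choosing the test from the data.** Picking the t-test or rank test by a Shapiro-Wilk check moved the error by at most about 0.4 percentage points from the t-test alone for normal scores. For log-normal scores it moved it by at most about 0.8 points above the rank test alone.

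**Text against text.** Section 3.3 excludes hypothesis testing, yet the secondary analyses prescribe a test for TMaP. This conflict does not depend on any assumed variance.

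**The case against.** The strongest case is that the defect is conditional and small. Section 5.1 allows a single therapist per site, and then the t-test is already a site-level test. The size depends on a between-site variance the protocol does not give, and at low values the error is only 5–6%. No alpha is claimed for this comparison. The text names neither a specific test nor independence, and a statistical analysis plan not shown might add a site term. Section 4.7 also has adherence monitored descriptively in the experimental arm, which this does not touch.

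Most of that stands, and it rules out several stronger readings a reader might infer:
- That the error rate is wrong in general. It is not wrong with one therapist per site.
- That with one therapist per site the comparison cannot reach significance. This is true only of the rank test at 3 v 3. The t-test can reach p < 0.05 there, and the rank test can at 4 v 4 and 5 v 5.
- That choosing the test from the data inflates the error materially. It adds little; its weakness is that 3–10 scores per arm cannot show the distribution.
- That unequal caseloads are a separate flaw which site summaries cure. Unweighted site proportions also give small and large sites the same weight.

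What does not stand is that this is mere silence. The protocol states a unit, a contrast and a type of test for TMaP, and extends its nested model by name to other secondary outcomes only. Nor would dropping the word test be enough, because a therapist-level 95% interval has the same shortfall: about 83–95% coverage under the 3-site settings above.

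**Conclusion.** The point holds in conditional form. Where sites contribute two therapists, the stated comparison overstates precision. With two at every site and assumed site SDs of 0–1.2, a nominal 5% t-test has a true error of about 5–17% (3 sites per arm) or 5–14% (5 sites per arm). It is 5–6% at site SD 0–0.2 and about 7–17% at 0.4–1.2. Site means hold about 5–6%. Mixed numbers of therapists give less inflation, and one per site gives none. These sizes rest on the assumed SDs, a 50% match rate and a 5% level.

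The conflict with section 3.3 is firm under any assumption, but it is an inconsistency of wording and does not itself show a unit-of-analysis error.

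Severity is low. TMaP is a secondary feasibility measure, and the primary RCSI analysis does not depend on it.

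**What to change.** In the secondary analyses, replace the distribution-dependent test. Suggested wording: *Among differential responders, the proportion whose selected therapy matches the algorithm's recommendation will be calculated for each site. The difference between arms in mean site proportion will be reported with a 95% confidence interval from the t distribution on the number of sites minus 2 degrees of freedom. No hypothesis test will be made. Therapist TMaP scores will be described by arm.*

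This puts the uncertainty at the level that was randomised, agrees with section 3.3 and removes the choice of test.

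The cost is analysis wording only; no data collection changes. The interval will be wider: the t multiplier is 2.78 on 4 df (3 sites per arm) or 2.31 on 8 df (5 sites per arm), against 2.23 on 10 df or 2.10 on 18 df for two therapists per site treated as independent. Sites of unequal size will count equally, so the number of differential responders per site should be shown beside each proportion.
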